7.5.3 Safety endpoints

Variables	Description	Scale	Time Window
Death	see primary endpoint above	0, no 1, yes	14±4 days
Unscheduled medical care	see primary endpoint above	0, no 1, yes	14±4 days
Unexpected Intensive Care Unit admission	see primary endpoint above	0, no 1, yes	24 hours
SAEs	Number and type of serious adverse events: 
 - Results in Death - Life-threatening illness or injury - Results in permanent disability / incapacity - Medical or surgical intervention to prevent life-threatening illness, injury or permanent impairment - Congenital anomaly / birth defect - Results in chronic disease - Requires hospitalisation or prolongation of existing hospitalisation 	0, no 1, yes	14±4 days

7.5.4 Covariates

Variables	Description	Scale	Time Window
Group allocation	control or intervention phase at time of inclusion	0, control phase 1, intervention phase	baseline
Phase	Number of phase at time of inclusion	Numeric, range 1-6	baseline
Age	Age in years	numeric	baseline
Sex	Sex	1, male 2, female	baseline
Chief complaint		0, fever 1, abdominal pain 2, syncope 3, non-specific complaint	
Triage level	Triage level	2-5	baseline
Admission type	Admission to the ED	0, Self-admittance 1, Ambulance 2, Air Rescue 88, other	baseline
Referral type	Type of referral to the ED	0, self-referral 1, GP 2, Hospital (intern) 3, Hospital (extern) 4, Air rescue (primary) 5, Ambulance (primary) 88, other	baseline
Charlson-Comorbidity-Index	Charlson Comorbidity Index (CCI) is Score of 19 comorbid conditions weighted from 1 to 6	Numeric, range 0-37	baseline
Confidence	Confidence regarding proposed primary diagnosis. (self-reported by the diagnosing physician via online survey)	Likert scale from 1 = not confident (50%) to 5 = confident (100%)	0-3 days
Difficulty	Perceived difficulty of the diagnostic reasoning process. (self-reported by the diagnosing physician via online survey)	Likert scale from 1 = difficult to 5 = easy	0-3 days
Familiarity	Familiarity/experience with the diagnosis (self-reported by the diagnosing physician via online survey)	Likert scale from 1 = not seen before to 5 = familiar	0-3 days
Typicality	Diagnosing physician judgement if the patient's presentation was atypical for the primary diagnosis.	0, typical 1, atypical	0-3 days
Diagnosing physicians	ED physicians (senior and resident) responsible for the treatment during patient's ED stay are recorded	Unique ID	length of ED stay, up to 24 hours
Age (physician)	Age in years	numeric	baseline
Sex (physician)	Sex of the diagnosing physician	1, male 2, female	baseline
Medical experience (physician)	Time of medical experience since obtaining the medical degree (years)	numeric	baseline
Emergency experience (physician)	Time of medical experience in emergency medicine (years)	numeric	baseline
Medical specialist (physician)	Medical specialist degree	0, no 1, yes	baseline

8 Sample Size

The sample size calculation has been performed for a multi-period cross-over cluster randomized controlled trial using according to Hemming at al. (2020) using the web-tool The Shiny CRT

Calculator.(4) The trial is designed to have a power of 80% to detect a clinically significant between-condition-difference in the primary outcome of 5 percent points on an alpha level of 0.05.

For the primary outcome, we assumed a positive composite score in 12% of the cases in the control condition. Further assumptions were a cross-sectional sampling and exchangeable correlation structure, an intra cluster correlation between 0.01 and 0.05, a coefficient of variation of cluster size of 0.5 and a 10% lost-to-follow up patients.

With 4 periods and 2 clusters (EDs) per sequence and the minimal sample size to detect a clinically significant between-condition-difference in the primary outcome of 5 percent points on an alpha level of 0.05 with a power of 80% equals to (in average) 74 patients per period and cluster and 1'184 patients in total. The sample size calculation was initially performed for 4 periods. However, the trial has been extended to 6 periods due to slow recruitment without modification of the overall required sample size.

9 General Analysis Considerations

9.1 Timing of Analyses

Once the study has been completed and all data have been entered and cleaned, a review of the data will be conducted and final changes will be made to this SAP. No efficacy analyses will be performed until the final version of this SAP has been approved. Any post-hoc, exploratory analyses not defined in this SAP will be clearly identified in the final report. Any deviations from the planned analyses detailed in this SAP will be documented with reasons in a post-analysis version of the SAP.

9.2 Analysis Populations

9.2.1 Intention to Treat (ITT) set

Data from all participant with or without protocol violation including dropouts and withdrawals will be included this analysis population.

9.2.2 Per Protocol (PP) set

Patients from the intervention group will be removed from the PP-analysis if no CDDS query has been documented. Vice versa, patients from the control group will be removed from the analysis if physicians self-report the query of any DDx generator outside the study protocol

9.2.3 Safety set

All subjects who received any study treatment (including control) and completed the study. Patients who did not complete follow-up will be excluded, except reason for non-completion is death.

9.2.4 Others:

None

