9.5 Interim Analyses

An interim analysis for safety outcomes was planned for the end of the second period.

As specified in the clinical investigation protocol (v1.5), safety outcomes are:

- Death within 14±4 days after ED (yes/no)
- Unexpected IMC admission within 24h after ED discharge if hospitalized (yes/no)
- Unscheduled medical care for the same complaints within 14±4 days after ED discharge (yes/no)
- Serious Adverse Events

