9.6 Multiple Testing

The primary endpoint is combined score of multiple secondary endpoints, for which we performed power analysis and determine the required sample size to detect a clinically relevant and statistically significant treatment effect. For the single analysis, no multiple testing needs to be performed. However, multiple sensitivity, subgroup and other hypothesis generating analyses will be performed (See section 11 Analysis). We do not plan any adjustments for multiple testing but rather discuss the issue of multiple testing in the limitation of the corresponding papers as appropriate.

10 Summary of Study Data

All continuous variables will be summarized using the following descriptive statistics: n (non-missing sample size), mean and standard deviation or median and quartiles as appropriate. The frequency and

percentages (based on the non-missing sample size) of observed levels will be reported for all categorical measures. In general, all data will be listed, sorted by site, treatment and subject. All summary tables will be structured with a column for each treatment in the order (Control, Experimental) and will be annotated with the total population size relevant to that table/treatment, including any missing observations. Summary reporting is subject to change based on Journals' requirement.

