10.1.3 Non completion

Reasons for non-completion of the study [non_comp_reason] are documented with following categories:

- 1 Patient withdrew consent
- 2 Patient was lost to follow-up
- 3 Patient was excluded requested by PI
- 4 Patient was excluded due to SAE
- 5 Patient died
- 88 Other reason

Patients who died before follow-up will not be considered as lost to follow-up. All others will be considered as lost to follow-up or drop outs.

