11.3 Exploratory Efficacy Analyses

An interaction term between treatment and the fixed effect covariates will be added to the primary efficacy model. Predicted probabilities for diagnostic risk with 95% confidence intervals will be shown for subgroups/covariates in case of any statistically significant interactions ($p < 0.05$). Additionally, interactions will also be performed for the analyses on the individual parameters of the composite primary endpoint score.

Additional exploratory analyses for secondary efficacy analyses or other endpoints may be conducted as appropriate. Any additional exploratory analyses will be appropriately labeled and clearly distinguished from planned analyses when results are reported in the clinical study report.

12 Safety Analyses

Serious adverse event incidences will be described using counts and proportions for each event category and treatment group (intervention and control). Each subject will only be counted once and any repetitions of serious adverse events will be ignored; the denominator will be the population size of the respective group. If multiple serious adverse event categories are checked for one single event, the event will be assigned to one category only in following order: Death; life-threatening illness or injury; permanent disability / incapacity; medical or surgical intervention to prevent life-threatening illness, injury or permanent impairment; Congenital anomaly / birth defect; Chronic disease; Hospitalization or prolongation of existing hospitalization.

(Serious) Adverse Events will be listed and described if a relation with the clinical investigational protocol or the medical device under investigation cannot be excluded.

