18.3 Table 2 – Primary and secondary efficacy outcomes

	Intervention Group		Control Group		Measure of effect	Adjusted effect (95% CI)	p value
	N	n (%) or median (IQR)	N	n (%) or median (IQR)			
Primary outcome							
Diagnostic quality risk	XXX	XX (XX%)	XXX	XX (XX%)	OR	X-XX (X-XX to X-XX)	<X-XXX
Secondary outcomes							
Death	XXX	XX (XX%)	XXX	XX (XX%)			
Unscheduled medical care	XXX	XX (XX%)	XXX	XX (XX%)	OR	X-XX (X-XX to X-XX)	<X-XXX
Unscheduled medical care within 7 days	XXX	XX (XX%)	XXX	XX (XX%)	OR	X-XX (X-XX to X-XX)	<X-XXX
Unscheduled medical care within 3 days	XXX	XX (XX%)	XXX	XX (XX%)	OR	X-XX (X-XX to X-XX)	<X-XXX
Unexpected ICU admission or upscale in care	XXX	XX (XX%)	XXX	XX (XX%)	OR	X-XX (X-XX to X-XX)	<X-XXX
Diagnostic discrepancy	XXX	XX (XX%)	XXX	XX (XX%)	OR	X-XX (X-XX to X-XX)	<X-XXX
ED costs in CHF	XXX	XX (XX to XX)	XXX	XX (XX to XX)	GMR	XX (XX to XX)	<X-XXX
Total hospital costs in CHF	XXX	XX (XX to XX)	XXX	XX (XX to XX)	GMR	XX (XX to XX)	<X-XXX
Safety Outcomes							
Serious adverse event (overall)	XXX	XX (XX%)	XXX	XX (XX%)			
Death							
Life-threatening illness or injury	XXX	XX (XX%)	XXX	XX (XX%)			
Permanent disability / incapacity	XXX	XX (XX%)	XXX	XX (XX%)			
Medical or surgical intervention to prevent life-threatening illness	XXX	XX (XX%)	XXX	XX (XX%)			
Injury or permanent impairment	XXX	XX (XX%)	XXX	XX (XX%)			
Congenital anomaly / birth defect	XXX	XX (XX%)	XXX	XX (XX%)			
Chronic disease	XXX	XX (XX%)	XXX	XX (XX%)			
Hospitalization or prolongation of existing hospitalization	XXX	XX (XX%)	XXX	XX (XX%)			

OR, Odds Ratio; GMR, Geometric Mean Ratio; ICU, intensive care unit; ED, Emergency department, CHF, Swiss Francs

18.4 Table 3 - Full-case review for diagnostic errors in a random subset. Items of the Safer Dx instrument compared between patients not randomly

		50 random patients with diagnostic quality risk	50 random patients without diagnostic quality risk	p value
Item 1	The documented history was suggestive of an alternate diagnosis, which was not considered in the diagnostic process.	XX (XX to XX)	XX (XX to XX)	<X-XXX
Item 2	The documented physical exam was suggestive of an alternate diagnosis, which was not considered in the diagnostic process.*	XX (XX to XX)	XX (XX to XX)	<X-XXX

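### The safety set leaves out surviving patients who exited because of a serious adverse event, and section 12 names no analysis set for the SAE table

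*SAP*

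**What the plan says.** Section 9.2.3 admits to the safety set those who received study treatment, control included, and completed the study. It then states: "Patients who did not complete follow-up will be excluded, except reason for non-completion is death".

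Section 10.1.3 gives the coded reasons for non-completion. Code 4 is "Patient was excluded due to SAE"; death is a separate code, 5. Patients who died are not treated as lost to follow-up, but for the remaining codes the rule is "All others will be considered as lost to follow-up or drop outs".

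The ITT set in section 9.2.1 is wider: data from all participants "including dropouts and withdrawals will be included this analysis population".

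Section 12 describes SAEs by counts and proportions per condition, and "the denominator will be the population size of the respective group". It names neither the safety set nor the ITT set. Section 12.1 sends the other safety endpoints to section 11.2.2, which uses the ITT set.

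**The concern.** A patient with code 4 has had an SAE by definition. The authors saw that one outcome-related exit, death, should not remove a patient from the safety set. They made no such allowance for the other outcome-related exit in their own code list. Fatal SAEs stay in the set, while a non-fatal SAE that ended participation leaves it. The same happens to any SAE recorded before a withdrawal, a loss to follow-up or an exclusion for another reason.

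Whether this reaches a reported number depends on section 12, which leaves the set open. Two analysts could follow the SAP faithfully and produce different SAE counts, rates and Ns from the same database. What is at stake is the between-condition comparison of SAE incidence in an open-label trial. The SAP lists SAE rates among its safety endpoints, so the population behind them should be fixed in advance and should not depend on the event being counted.

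**Working it through.** **Step 1. Who is in which set** (sections 9.2.1, 9.2.3 and 10.1.3 side by side; enrolled patients who were managed in the ED):

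| Exit | Safety set | ITT set |
|---|---|---|
| Completed follow-up | in | in |
| Died (code 5) | in, by the exception | in |
| Excluded because of an SAE, alive (code 4) | out | in |
| Other non-fatal exit (codes 1, 2, 3, 88), SAE already on file | out | in |

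The last row can occur: the schedule in section 7.4 records SAEs during examination and ED stay as well as at follow-up, so an SAE can be in the data before the patient leaves.

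**Step 2. Where the safety set is used.** Death, unscheduled care and ICU admission go through 12.1 to 11.2.2 and so to the ITT set. That leaves SAE incidence as the only final safety analysis for which the safety set could be meant, but section 12 does not name it. No other section assigns an analysis to it. Section 10 has summary tables "annotated with the total population size relevant to that table/treatment, including any missing observations", which still leaves open which population is relevant. The Table 2 shell gives the SAE rows their own N column without naming a set. Two readings remain:

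- SAE table on the safety set: the last two rows of the table above drop out of the numerator and the denominator.
- SAE table on the ITT set: no SAE is lost, and 9.2.3 is a definition without a stated use.

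**Step 3. Scale.** Inputs: planned total 1,184 (section 8) and 10-15% expected missing primary outcome through drop-out, withdrawal and loss (section 9.4.1). An equal split between conditions is assumed.

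- The plan's own total: 74 patients × 4 periods × 4 clusters = 1,184, which agrees with section 8.
- Outside the set: 1,184 × 0.10 = 118; 1,184 × 0.15 = 178, less any deaths counted among them. These are expected values, not bounds. Some of these patients may be outside the set anyway, because section 18.1 counts as drop-outs patients who left before clinical examination.
- Left in the set: 1,184 × 0.90 = 1,066; 1,184 × 0.85 = 1,006, or about 533 to 503 per condition, against 1,184 / 2 = 592 on the ITT set.
- One patient with an SAE is then worth 1/533 = 0.19 to 1/503 = 0.20 percentage points in that condition's rate.

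**Step 4. Direction.** Let p be the share of all patients removed by the completion rule and q the share of SAE patients removed. The safety-set rate divided by the rate in all patients is (1 − q)/(1 − p). It falls below 1 only if q exceeds p. The SAP gives no value for q. An illustration with assumed counts, 592 per condition, 30 patients with an SAE and p = 10%, shows both directions:

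- ITT set: 30/592 = 5.1%.
- One SAE patient removed: 29/533 = 5.4%, higher than ITT.
- Five SAE patients removed: 25/533 = 4.7%, lower than ITT.

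The counts 30, 1 and 5 are not in the SAP and carry no evidential weight. They show only that the sign cannot be fixed in advance.

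**The case against.** The strongest reply is that the population size of a group may simply mean everyone allocated to a condition. Allocation is fixed at inclusion (section 7.5.4), section 10 counts missing observations in the table totals, and 12.1 already leads to the ITT set for the other safety endpoints. On that reading no SAE is lost and 9.2.3 is a leftover. This is plausible, and it is why the selection problem is stated only conditionally. It does not settle the matter, because section 12 never says so and a separately defined safety set suggests the opposite.

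A second reply is that a completer rule has a rationale: patients whose 14±4-day SAE status is unknown would otherwise count as event-free. That stands as a reason to show a completer-based rate as well. It does not justify leaving out patients whose SAE is already known.

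A reader might go further and infer that the plan hides SAEs, or that its safety conclusions are biased in favour of the intervention. The SAP does not support this. Section 10 says that, in general, all data will be listed, and section 12 lists events whose relation to the protocol or the device cannot be excluded; neither carries a completion condition. No expected number of code-4 exclusions is given, and nothing indicates that they would differ by condition. A reader might also extend the point to the interim safety comparison in section 9.5. That section names no set either, but it describes a descriptive comparison without a formal stopping rule, and nothing in it ties the comparison to 9.2.3.

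**Conclusion.** The point holds as a defect of definition and should be fixed. As written, 9.2.3 with 10.1.3 removes from the safety set surviving patients who have an SAE by definition, and section 12 leaves open whether that set is used. If it is, the final descriptive SAE comparison is selected on a safety outcome. If it is not, the definition is idle.

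The consequence is confined to one descriptive table. The primary analysis and the ITT analyses of death, unscheduled care and ICU admission are unaffected. The number of SAE patients removed is unknown and may be zero, and the direction of bias is unknown. The figures of 118 to 178 patients outside the set and 503 to 533 per condition inside it rest on the SAP's expected non-completion and an assumed equal split. They show scale and do not estimate bias.

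**What to change.** Delete the completion requirement in 9.2.3. Define the safety set as all enrolled patients managed in either condition, analysed by condition, with recorded SAEs counted up to the last available information (after a withdrawal, as far as consent allows). In section 12, name this set for both numerator and denominator of the SAE table, and show its N in Table 2.

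The cost is a few sentences of SAP text and one analysis flag. SAEs and reasons for non-completion are already recorded, and section 9.1 provides for final SAP changes before the efficacy analyses.

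The drawback is that non-completers with unobserved follow-up enter the denominator. If they have the same underlying SAE rate as completers and none of their SAEs is recorded, the rate is multiplied by 1 − p, that is 0.90 to 0.85 at 10-15% non-completion. A supplementary completer-based rate would show how much this matters; it is optional.

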9.3 Covariates and Subgroups

Subgroup analyses and treatment interactions will be assessed with following covariates/subgroups:

- Patient characteristics (Age, sex, chief complaint)
- Disease characteristics: confidence, difficulty, familiarity, typicality
- Physician characteristics: medical experience, emergency experience, medical specialist

All analyses on interactions and subgroups are explorative and described in section 11.3 or 13.

9.4 Missing Data

9.4.1 Missing outcome data

The amount of missing data for the primary endpoint is anticipated to correspond to the number drop-outs, withdrawal and lost-to-follow up (10-15% expected).

9.4.2 Missing covariate data

We expect very low missing covariate data as used in primary efficacy analyses. Missing rates of 5% and lower were discussed to have no consequences on the estimates. (5) Therefore, missing data will be handled with full information maximum likelihood estimation. In case of a missing data rate of above 5%, we will repeat the primary efficacy analysis after multiple imputation as sensitivity analysis.

9.5 Interim Analyses

An interim analysis for safety outcomes was planned for the end of the second period.

As specified in the clinical investigation protocol (v1.5), safety outcomes are:

- Death within 14±4 days after ED (yes/no)
- Unexpected IMC admission within 24h after ED discharge if hospitalized (yes/no)
- Unscheduled medical care for the same complaints within 14±4 days after ED discharge (yes/no)
- Serious Adverse Events

9.5.1 Purpose of Interim Analyses

Based on the evaluation, the sponsor investigator and local PIs decided whether the clinical trial has to be stopped or continued

9.5.2 Planned Schedule of Interim Analyses

After study end of the last included patient of period 2.

9.5.3 Stopping Rules

No formal stopping rules were set a priori. Decision is based on clinical judgement of the sponsor - investigator and local PIs.

9.5.4 Analysis Methods

Safety outcomes were compared between intervention and control periods and between sites using descriptive statistics.

9.5.5 Practical Measures to Minimize Bias

Safety interims analysis is performed by one of the trial statistician and data manager ([name]) who is unblinded at any time of the trial. However, the safety interim analysis does not include any efficacy analysis of the primary endpoint and the final analysis will be performed by an external statistician not involved in any study procedure ([name]). Therefore, no additional measures are required to minimize bias (see section 15).

9.5.6 Documentation of Interim Analyses

Snapshot of the data available at the safety interim analysis, script for statistical analysis and report for the sponsor and principal investigators is preserved.

9.6 Multiple Testing

The primary endpoint is combined score of multiple secondary endpoints, for which we performed power analysis and determine the required sample size to detect a clinically relevant and statistically significant treatment effect. For the single analysis, no multiple testing needs to be performed. However, multiple sensitivity, subgroup and other hypothesis generating analyses will be performed (See section 11 Analysis). We do not plan any adjustments for multiple testing but rather discuss the issue of multiple testing in the limitation of the corresponding papers as appropriate.

10 Summary of Study Data

All continuous variables will be summarized using the following descriptive statistics: n (non-missing sample size), mean and standard deviation or median and quartiles as appropriate. The frequency and

percentages (based on the non-missing sample size) of observed levels will be reported for all categorical measures. In general, all data will be listed, sorted by site, treatment and subject. All summary tables will be structured with a column for each treatment in the order (Control, Experimental) and will be annotated with the total population size relevant to that table/treatment, including any missing observations. Summary reporting is subject to change based on Journals' requirement.

